#### **Assessment of Seriousness**

"Seriousness" is based on patient/event outcome or action criteria usually associated with events that pose a threat to a patient's life or functioning. "Seriousness" (not severity) serves as a guide for defining regulatory reporting obligations for Serious Adverse Events (SAE).

## 7.4.3. Reporting Serious Adverse Events (SAEs)

All SAEs occurring during study participation must be reported **immediately (within 24 hours)** to the Sponsor representative (or designee), and then to the governing IRB/IEC as required by the IRB/IEC, local regulations, and the governing health authorities.

Prompt notification of SAEs by the Investigator to the appropriate Sponsor contact for SAE receipt is essential so that legal obligations and ethical responsibilities towards the safety of other patients are met. Any Unexpected SAE which is attributed to investigational product (SUSAR) requires immediate notification to the regulatory agencies. The full report will be sent to the regulatory agencies within the regulatory timelines. The Sponsor should also expedite the safety reporting to all concerned investigator/institutions, to IEC/IRB and regulatory agencies according to the local regulatory timelines.

# 7.4.3.1. Notification of the SAE and Transmission of the SAE Report

Once an investigator becomes aware that an SAE has occurred, he/she must report the information to the Sponsor (or designee) within 24 hours. The SAE form will always be completed as thoroughly as possible with all available details of the event, signed by the Investigator and forwarded to the Sponsor (or designee) within the designated time frames. If the Investigator does not have all information regarding an SAE, he should not wait to receive additional information before notifying the event and completing the form. The form will be updated when additional information is received. Whenever possible, the Investigator will provide an assessment of causality at the time of the initial report as described above.

After the initial report, the SAE should be promptly followed by a detailed writing report including all data allowing to document the event and notably the anonymous copies (with patient study number) from hospitalization's report and any additional examination(s) performed.

For reported death, the Investigator should provide any additional requested information such as autopsy reports if available and terminal medical reports.

## 7.4.3.2. SAE waived from expedited regulatory reporting to regulatory authorities

For the purpose of the study the following events will not be designated as a SAE:

- hospital admission as a part of the normal planned treatment or monitoring of the studied indication and not associated with any deterioration in condition,
- hospitalization planned before inclusion in the study,
- admission for diagnostic evaluation of an AE,
- overnight hospitalization due to social or travel reasons.

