## 7.4.1.2. Serious Adverse Event (SAE) or Serious Adverse Drug Reaction (Serious ADR)

A serious AE or drug reaction or any untoward medical occurrence that, at any dose, has one or more of the following attributes:

- Results in death.
- **Is life-threatening,** which means that the patient is at immediate risk of death at the time of the SAE; it does not refer to a SAE that hypothetically might have caused death if it was more severe.
- Requires inpatient hospitalization or prolongation of existing hospitalization. Hospitalization is defined as inpatient care that covers more than one calendar day.
- **Results in persistent or significant disability/incapacity**, which means that there is a substantial disruption of a person's ability to carry out normal life functions.
- Is a congenital anomaly/birth defect.
- Is medically important, defined as an event that may jeopardize the patient or may require medical or surgical intervention to prevent one of the outcomes listed above, or result in urgent investigation. Examples of such medical events include allergic bronchospasm requiring intensive treatment in an emergency room or at home, blood dyscrasias or convulsions that do not result in patient hospitalization.

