## 7.4.2. Procedures for recording, analyzing and reporting AEs

# 7.4.2.1. Monitoring and recording of AEs

At each visit, occurrence of AEs will be assessed by verbally asking the patients if they have had any problems or symptoms since their last visit.

For each AE, regardless of the suspected causal relationship to study drug, the Investigator has to report on the AE page(s) of the eCRF the relevant information of the AE including the nature, the anteriority (emergent or not), the timing of event occurrence and resolution, the frequency (intermittent or continuous), the severity (mild, moderate, severe), the relationship with the study drug, and actions taken to treat the adverse experience. The Investigator has also to pursue and obtain adequate information in order to determine the outcome of the AE and also to assess the seriousness, i.e. whether it meets the criteria for classification as a SAE requiring immediate notification to the Sponsor.

Whenever possible, a unifying diagnosis should be recorded in the eCRF as the AE rather than individual signs or symptoms. Similarly, the unifying diagnosis should be recorded as the AE rather than the abnormal laboratory result (i.e. "anemia" instead of "low hemoglobin"). If the AE is a worsening of a past medical condition, the AE should clearly indicate that the past medical condition has worsened using words such as "worsening," "aggravated," or "exacerbation."

AEs will be coded according to the Medical Dictionary for Regulatory Activity (MedDRA current version). AEs will be individually listed per patient number, presenting System Organ Class (SOC), preferred term, emergence, description, date and time of onset, date and time of last study drug administration before AE, duration, time from onset since last study drug administration, frequency, severity and seriousness, relationship to study drug, the required action taken (corrective treatment, hospitalization), and outcome if any.

All AEs (including SAEs) must be followed until satisfactory resolution or stabilization.

Any AE and any measure taken and follow-up result must be recorded in the patient's eCRF, as well as in the patient's source document. Follow-up laboratory results should be filed with the patient's source documentation.

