#### 4.10.1 Adverse events

Adverse events (AEs) will be presented by MedDRA System Organ Class (SOC) and Primary Term (PT). Coding of verbatim terms will be performed by Ergomed and all relevant codes are stored in the database and it will be approved by the Sponsor before database lock (cf. DMP).

Only treatment-emergent adverse events (TEAE) will be analysed, i.e. all new and worsened pre-existing adverse events occurring on or after the initiation of IMP. It is assumed that for each change in intensity, relationship, or seriousness of an AE a new entry of the AE was recorded in the data capture database; hence such cases will be analysed like different phases of the same AE.

An overall summary of TEAEs will be presented including both the number and percentage of patients with a given AE category and the number of events:

- All TEAEs
- Serious TEAEs (STEAEs)
- Treatment-related TEAEs
- Treatment-related Serious TEAEs
- Severe TEAEs
- TEAEs leading to study drug discontinuation
- Fatal TEAEs

A descriptive analysis will be performed. Global incidences of primary system organ classes (SOC) and preferred terms (PT) will be calculated for:

- All TEAEs irrespective of the causality assessment
- Serious TEAEs (STEAEs)
- TEAEs by relationship
- STEAEs related to study drug
- TEAEs by maximum severity
- TEAEs leading to discontinuation
- Fatal TEAEs

Statistical Analysis Plan	Version 1.0		Page 26 of 37
Sponsor	SOM Biotech	Protocol No	SOMCT03

These tables will be presented by treatment group and also include summary lines for all SOCs and the occurrence of any event of the specified type. SOC terms will be presented according to the Internationally Agreed Sorting Order (MedDRA).

Multiple counts within a PT or SOC (repeated or different included terms or changes in descriptors) will be counted only once for the calculation of incidences. In addition to the incidences, the number of reported AEs (within a PT or SOC) will be included in the summaries.

Detailed listings of all fatal and other serious events will be provided (for section 14.3.2). All adverse events (i.e. TEAEs as well as non-treatment emergent events) will be listed in section 16.2.

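### Protocol 7.4.3.2 removes the SAE designation from AE-driven diagnostic admissions that 7.4.1.2 classifies as serious, so serious events can be under-classified

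*Protocol*

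**What the plan says.** Protocol 7.4.1.2 gives the criteria for a serious adverse event. One is that the event "Requires inpatient hospitalization or prolongation of existing hospitalization". The section then sets the threshold: "Hospitalization is defined as inpatient care that covers more than one calendar day". It makes no exception for the purpose of the admission. The criterion for medically important events also takes in those that may "or result in urgent investigation".

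Protocol 7.4.3.2 is headed "SAE waived from expedited regulatory reporting to regulatory authorities". Its opening sentence goes further: "For the purpose of the study the following events will not be designated as a SAE". Four kinds of admission follow. Three are planned monitoring without deterioration, stays arranged before inclusion, and overnight stays for social or travel reasons. The fourth is "admission for diagnostic evaluation of an AE", without qualification.

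Under Protocol 7.4.2.1 the investigator judges for each AE "whether it meets the criteria for classification as a SAE requiring immediate notification to the Sponsor". Protocol 7.4.3 and 7.4.3.1 require SAEs to reach the sponsor within 24 hours, and 7.4.3 handles a SUSAR as an unexpected SAE attributed to the product. SAP 4.10.1 tabulates serious TEAEs, overall and by relationship to treatment, and provides detailed listings of fatal and other serious events.

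**The concern.** The heading of 7.4.3.2 presupposes that the listed events are SAEs and only relaxes how fast they go to authorities. The text takes the SAE designation away. These differ in effect: a waived SAE stays in the SAE data and tables, whereas an event that is not designated never enters them.

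The diagnostic-evaluation item is also unlike the other three. Those admissions are not responses to a new event. This one, by its own terms, is caused by an adverse event.

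What is at stake is the completeness of serious-event reporting. Safety is a secondary objective, with particular attention to depression and suicidality and to cardiovascular haemodynamics. The protocol expects bradycardia and hypotension as effects of the drug, and such events could plausibly lead to admission for work-up. Sites that resolve the conflict differently would also make SAE counts inconsistent between centres.

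**Working it through.** The plan states no figure on this point, so there is nothing to reproduce. The check is a comparison of the two sections, followed through to the outputs.

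**Classification by case**

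| AE leading to a diagnostic admission | 7.4.1.2 | Text of 7.4.3.2 | Heading of 7.4.3.2 |
|---|---|---|---|
| Stay over one calendar day, no other criterion met | Serious (hospitalisation) | Not an SAE | SAE, expedited reporting waived |
| Stay within one calendar day, no other criterion met | Not serious | Not an SAE | Not applicable |
| Any stay, event may lead to urgent investigation | Serious (medically important) | Not an SAE as written | SAE, expedited reporting waived |
| Any stay, another criterion met, such as life-threatening | Serious | Silent; presumably stays serious | Unclear |

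The first row is a direct contradiction. The second is not, so on the hospitalisation criterion the conflict is confined to longer stays. The third and fourth rows show a gap: 7.4.3.2 has no clause that keeps an event serious when it meets another criterion, and neither section states precedence.

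**Consequences**

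1. The investigator assigns seriousness (7.4.2.1). One who follows 7.4.3.2 as written records the event as non-serious.
2. A non-serious event does not trigger 24-hour notification (7.4.3, 7.4.3.1), and it cannot become a SUSAR, because that route starts from an SAE.
3. SAP 4.10.1 describes no re-derivation of seriousness, so the event is absent from the serious TEAE tables and listings.

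**Direction.** The exclusion can only take events out of the set defined by 7.4.1.2. Relative to that section, the SAE count can fall but cannot rise.

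**Size.** The documents give no rate of diagnostic admissions. For scale only, let q be an assumed per-patient risk of an AE-driven diagnostic admission of more than one calendar day, with N = 129 (Protocol 9.3). The expected number is N × q, and the chance of at least one is 1 − (1 − q)^129.

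| Assumed q | Expected number | Chance of at least one |
|---|---|---|
| 0.5% | 129 × 0.005 = 0.65 | 48% |
| 1% | 129 × 0.01 = 1.29 | 73% |
| 2% | 129 × 0.02 = 2.58 | 93% |
| 5% | 129 × 0.05 = 6.45 | above 99% |

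None of these risks comes from the documents. The table shows only that the answer ranges from probably none to several, depending on an unknown.

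**The case against.** The strongest reply is that all four items in 7.4.3.2 are admissions, not medical events. On that reading, the admission alone does not confer seriousness, and the underlying AE is still judged against the remaining criteria, including urgent investigation. This is a reasonable reading, but 7.4.3.2 does not state it. Even if it were adopted, the hospitalisation criterion of 7.4.1.2 would still classify the longer stays the other way.

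The second reply is that the events are not lost, and this stands. Every AE is recorded, and Protocol 7.4.2.1 lists hospitalisation among the actions taken, so affected cases could be traced. The SAP tabulates all TEAEs, severe TEAEs, related TEAEs and those leading to discontinuation. Vital signs are summarised separately, and ECGs are read centrally. The cardiovascular objective does not rest on the serious-event table alone.

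A reader might also infer three stronger conclusions, which the documents do not support:

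- **Serious events will be under-counted.** Without an admission rate, only the direction is known.
- **The missing events would differ between arms.** No admission rates by arm are given, and the rule applies equally under the blind.
- **The DSMB would not see these events.** Protocol 7.4.5 and SAP 1.3 give it safety data without restriction to SAEs, and its charter is not among the documents.

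**Conclusion.** The contradiction is real, both between 7.4.3.2 and 7.4.1.2 and between the heading and text of 7.4.3.2. For an AE that leads to a diagnostic admission of more than one calendar day, one section says serious and the other says not. Where an event may lead to urgent investigation, the conflict can extend to shorter stays.

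The supported conclusion is that serious events can be under-classified relative to 7.4.1.2 and can then miss 24-hour notification, SUSAR assessment and the serious TEAE tables. It assumes that at least some investigators apply 7.4.3.2 as written and that the SAP takes seriousness as recorded. The number affected cannot be determined. The overall TEAE tables and the primary analysis are untouched. The point should be corrected because the rule is wrong as written and cheap to repair.

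**What to change.** Reconcile Protocol 7.4.3.2 with 7.4.1.2 so that one definition decides seriousness:

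- State whether the list in 7.4.3.2 waives only expedited reporting or removes the SAE designation, and make its heading and text agree.
- State that an AE meeting any criterion in 7.4.1.2 is recorded as serious, whatever the purpose of the admission.
- In SAP 4.10.1, tabulate every such TEAE as serious, and flag separately any admission waived from expedited reporting.

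The cost is a protocol wording change and a few more SAE forms. If seriousness is to be re-derived for patients already enrolled, length of stay and the criterion met must be available. The documents do not show that the eCRF captures them, so they may need to be added or queried. Treatment, visits and sample size do not change.

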## 7.4.4. Procedures for Reporting Pregnancy Exposure and Birth Events

The Investigator must promptly report all pregnancies to the Sponsor (or designee). While the pregnancy itself is not considered to be an AE or SAE, any pregnancy complications should be recorded as AEs or SAEs. Any pregnancy should be followed through its conclusion for observation of any congenital anomalies or birth defects which are a SAE.

## 7.4.5. Data Safety Monitoring Board (DSMB)

According to ICH E6, an independent Data Safety Monitoring Board (DSMB) will be established to assess at intervals the progress of the clinical trial, safety data, and recommend to the Sponsor whether to continue, modify or terminate a trial. The DSMB will have written operating procedures and maintain records of all its meetings, including interim results; these should be available for review when the trial is complete. The independence of the DSMB is intended to control the sharing of important comparative information and to protect the integrity of the clinical trial from adverse impact resulting from access to trial information. The DSMB is a separate entity from an IRB or an IEC, and its composition should include clinicians and clinical trial scientists knowledgeable in the appropriate disciplines including statistics.

A charter will define clearly the roles and responsibilities, the membership (with independent experts in the clinical aspects of the disease and one biostatistician), and organization of the meetings. The procedures should also address the way to keep confidential the data analyzed, the voting rules and the control of dissemination of interim trial results within the Sponsor organization.

## 7.5. PK-PD ASSESSMENTS

#### 7.5.1. SOM3355 plasma concentration

Blood samples for PK will be obtained in all patients at each visit under active treatment with SOM3355 (or placebo) from Visit 2 to Visit 5 for measurement of **SOM3355 (bevantolol) plasma concentration** at trough (pre-dose), and also 2 hours after dosing at Visit 2 and Visit 4.

Complete information on blood sampling, conditions of plasma preparation and storage, as well as shipment details and central laboratory contact details will be supplied in a separate technical brochure provided by the central laboratory.

Drug quantification will be performed using a validated bioanalytical method based on ultra HPLC coupled to tandem mass spectrometry (UHPLC-MS/MS).

# 7.5.2. Prolactin plasma level

An increase in prolactin plasma levels was observed with SOM3355 administration in the previous Phase 2a POC study, consistent with that seen with other VMAT2 inhibitors like tetrabenazine. However, the increase was found not to be dose-proportional with SOM3355 levels, showing a mean increase of 1.7- and 1.9-fold at the 100 mg and 200 mg BID doses, respectively (SOMCT02 – PK/PD Report). This may reflect changes in dopaminergic tone in the hypothalamus and/or pituitary gland (Orrillo et al, 2020). Therefore, prolactin plasma levels could be considered as a biomarker of the pharmacodynamic (PD) effect of SOM3355.

Blood samples will be obtained at each visit from Visit 1 to Visit 6 in all patients to measure prolactin plasma concentration, before dosing at each visit and 2 hours after dosing at Visit 2 and Visit 4. Prolactin plasma quantification will be determined by chemiluminescence technique.

Samples will be collected and stored with the PK samples and analyzed by the central laboratory in order to keep the blind during the study.

## 7.5.3. *PK sub-study*

A PK sub-study will be conducted to characterize the PK profile of repeated doses of SOM3355 at 400 and 600 mg/day. This analysis will be performed by collecting 12-hour PK samples (H0 before dosing, H0.5, H1, H1.5, H2, H3, H5, H8, H12) in 8 patients per arm (24 patients in total) that will be hospitalized for 24 hours at Visit 2.

These patients will be recruited by 3-4 sites able to manage the logistic of PK sampling. PK sub-study data will be collected in an independent database and analyzed as soon as possible, before the end of the clinical trial. Complete information on blood sampling, conditions of plasma preparation and storage, as well as shipment details for PK sub-study and central laboratory contact details will be supplied in a separate technical brochure provided by the central laboratory.

In addition, cardiac and hemodynamic parameters will be collected in parallel to allow PK-PD modeling assessments. For this, the patients will have cardiac Holter monitor placed on the chest to record ECG during the 12 hours of plasma sampling, allowing to analyze ECG parameters at the same time points than PK samples, and blood pressure will be measured 5 minutes before each PK sample (the patient resting quietly in a comfortable sitting position, his/her back and arm supported with the middle of the upper arm at heart level, legs uncrossed, and feet flat on the floor).

# 8. CONDUCT OF THE STUDY

For each participant, the total treatment duration, from the inclusion visit, will be 12 weeks (+ 1 or 2 weeks for screening before inclusion) with a total of 7 visits.

The visit schedule and procedure assessments are listed in section 1.3.

This is an outpatient study, except for 24 patients that will be enrolled in the PK sub-study who will be hospitalized for 24 hours at Visit 2. HD patients come to visit their specialist at the hospital on successive time-points. All visits must be performed by investigators and sub-investigators qualified for this study and who are experts in the management of HD patients.

Visits are scheduled as follows:

•	V0 -	Screening visit:	at Day -7 to -14 max (Week -1 to -2 max)
•	V1 -	Inclusion visit (randomization):	at Day 0 (Week 0)
•	V2 -	End of up-titration:	at Day $21 \pm 2$ Days (Week 3)
•	V3 -	Interim visit at maintenance dose:	at Day $42 \pm 2$ Days (Week 6)
•	V4 -	End of maintenance dose #1	at Day $63 \pm 2$ Days (Week 9)
•	V5 -	End of maintenance dose #2	at Day $70 \pm 2$ Days (Week 10)
•	V6 -	End of study	at Day $84 \pm 2$ Days (Week 12)

If the date of one visit is changed (anticipated or delayed), the next visit should occur according to the original schedule.

# 8.1. STUDY PROCEDURES AT EACH VISIT

# 8.1.1. Visit 0 - Screening visit – within 14 days before inclusion

The eligibility of the patients will be assessed during the screening period that starts with the Screening Visit within 1 or 2 weeks before the inclusion. The duration of the screening period is up to 2 weeks and must be long enough to establish inclusion/exclusion criteria from Visit 0 to the inclusion visit (i.e. Visit 1 at Day 0).

At Visit 0, the Investigator must first obtain the patient informed consent as described below, and then check that he/she meets all the inclusion criteria and none of the exclusion criteria.

#### Obtaining the Patient informed consent

If a patient is eligible to be enrolled in the study, prior to conduct of any study-specific screening procedures, the Investigator, or designee, will explain to the patient the study procedures, including the risks involved and the fact that its participation is voluntary.

The Investigator should give to the patient the study's IRB/IEC-approved written informed consent form (ICF) and orally present all necessary information to the patient, in order to enable him/her to make an informed and unconstrained decision about participating in the study. An appropriately

signed ICF will be obtained prior to entry into the study for each patient who has made the decision to participate. Information regarding the collection of the patient informed consent should be registered in the source document (date, protocol number, and name of the Investigator or sub-investigator who has informed the patient).

In addition, the following assessments must be performed at Visit 0, and information must be collected and documented in the CRF within the screening period:

- Patient medical history and history of HD diagnosis, with documented genetic diagnosis;
- Patient history of all the treatments must be notified in the source documentation prior to randomization (with regimen, duration, and complications and their treatments);
- Demographics characteristics (age, gender, and ethnic origin);
- Physical and neurological examinations with the presence of chorea symptoms;
- Vital signs (SBP, DBP, orthostatic BP, and heart rate measured according to the standardized method described in section 7.3.3), body height and weight;
- List of current concomitant medications;
- Clinical scores and functional tests: UHDRS®-Motor part (including TMS and TMC, gait and dystonia sub-scores), UHDRS®-Total Functional Capacity, UHDRS®-Functional assessment, and C-SSRS, BDI, and ESS;
- 12-lead ECG (sent for centralized reading by a cardiologist);
- Safety laboratory tests (chemistry, hematology) analyzed by local laboratory (including a pregnancy test if female of childbearing potential).

